1 INTRODUCTION

This document outlines the initial plan for the summarization and analysis of clinical data collected in STUDY 0145 for TD-9855, Part C only.

This is the proof of concept study to determine if the norepinephrine reuptake inhibitor TD-9855 produces an acute pressor effect in patients with primary forms of autonomic failure, and if this is associated with a reduction in symptoms of orthostatic intolerance. Results of this study will guide decisions about the further development.

This document describes the a priori plan for analysis. Once the analysis is in progress, it may become apparent from the data that the planned analysis should be modified. Any substantive modification to the original analysis plan will be identified in the clinical study report (CSR).

2 STUDY OBJECTIVES

2.1 Primary Objective

The primary objective of the study is to determine if TD-9855 has sustained pressor response and improves symptoms of orthostatic intolerance in subjects with nOH due to MSA, PAF, or Parkinson's disease.

2.2 Secondary Objectives

The secondary objectives of the study are:

[figure not shown]
- to evaluate the safety and tolerability of TD-9855 in the control of nOH. and
- to evaluate the PK and PD (NE and DHPG) of TD-9855 after single and multiple doses in subjects with nOH.

3 OVERVIEW OF STUDY DESIGN

[figure not shown]
This is a multicenter, randomized, 3 part, single-blind (Part A), double-blind (Part B), and open-label multiple dose extension (Part C) study of TD-9855 versus placebo in subjects

with nOH. However, beginning with Amendment 2 of this protocol, Part B of the study has been discontinued.

This study consists of three Parts, A, B and C. Part A follows a daily, single, escalating dose design starting with placebo on Day 1, followed by a dose of TD-9855 on Day 2, and proceeding to escalating higher doses of TD-9855 on a daily basis up to a max dose of based on safety, tolerability, and determination of a pressor effect. Starting from protocol Amendment 2, TD-9855 escalation doses changed to Day 5.

Part B follows a randomized, placebo—controlled, parallel design evaluating a dose that was determined to be generally well tolerated and to have a pressor effect for a given subject from Part A.

[figure not shown]

-		•		A, who complete			
remain otherwis	_	-		Part C and rece	ive open-label		
1D-9855 by tab	TD-9855 by tablet once daily for up to						
For subjects en	rolled under An	nendment 2, the	e dose administ	ered on Day 2 c	of Part C will be		
-				stered on Day			
(rounded up to	the nearest 1 m	ng). Subjects wi	ill continue rece	iving the dose le	evel from Day		
2 of Part C for t	he remainder o	f the study. How	wever in the cas	se where a subj	ect develops		
the presence or	worsening of p	reviously descr	ibed supine hyp	pertension or oth	ner adverse		
events suggest	ing intolerability	,					
				l.			
Under Amendm	nent 3 subjects	will be dischard	ed from the res	search clinic on	Day 2 and		
	•	_		bsequent sched			
		•		dose level at the			
•	•	•	•	e, a higher dose			
Day 29, dose in	creases will ne	ed to be discus	sed with the Sp	onsor. It is reco	mmended that		
the subject rece	eives at least 7	daily doses of T	D-9855 at any	single dose leve	el before		
escalation to a	higher dose to a	allow TD-9855 e	exposure to rea	ch steady state	at the lower		
dose.							
			. The	e schedule for p	otential dose		
increases is she	own in the table	below.					
Part A	Dort C Doy 1	Dort C Doy 9	Dort C Dov	Dort C Dov	Dort C Dov		
Maximum	Part C Day 1 dose	Part C Day 8 dose	Part C Day 15 dose	Part C Day 22 dose	Part C Day 29 dose		
Dose	uose	uose	13 4036	22 0036	29 0036		

Part A Maximum Dose	Part C Day 1 dose	Part C Day 8 dose	Part C Day 15 dose	Part C Day 22 dose	Part C Day 29 dose

In the case where a subject develops the presence or worsening of supine hypertension (as determined by the Investigator with agreement from the Sponsor) or other adverse events suggesting intolerability,

Regardless of the protocol amendment, if supine hypertension or other adverse events persist after the dose has been reduced, dosing in that subject should be discontinued and appropriate alternative therapy and care provided to the subject as determined by the principal investigator.

4 SAMPLE SIZE AND POWER

[figure not shown]

Table 1. Sample size for Part C

5 STUDY ENDPOINTS

5.1 Efficacy Endpoints

For Part C, the primary endpoint is the improvement from baseline in the Likert scale "dizziness, lightheadedness, feeling faint, or feeling like you might black out" (OHSA, question 1) at week 4.

The secondary endpoints for Part C include:

- Change from baseline in the composite OHSA, OHDAS, and OHQ score
- Change from baseline in standing SBP
- Change from baseline in seated SBP
- Duration of standing during the orthostatic standing test
- Change from Supine SBP to Seated SBP

5.2 Safety Endpoints

For all Parts of the study, safety and tolerability assessments will include adverse events, laboratory abnormalities, ECGs, and vital sign measurements including supine blood pressure.

6 GENERAL ANALYSIS CONSIDERATIONS

6.1 Global Definitions and Conventions

All data from scheduled and unscheduled visits will be presented in the subject listings; however, unless noted otherwise, only data from scheduled visits will be included in the summaries, statistical analysis, and calculation of derived parameters.

6.2 Baseline Definition

For the OHQ (OHSA and OHDAS) scores and Clinician's/Subject's Global Impression, baseline is defined as the pre-lunch measurement on Day -1. For the blood pressure, heart rate, and duration of standing, baseline is defined as the pre-breakfast measurement on Day 1. For laboratory abnormalities and ECGs, baseline is defined as the measurement on Day -1.

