Visit number	Admit		Treatment period									Follow-up		
	1		2	3	4	5	6	7	8	9	10	11 EOS		
Study week (beginning of week except Day 140)				1	2	3	4	5	9	13	17	20	23	25
Procedure (Study Day)	Admit Day -2	Day -1 ^b	Day 1 ^b	Day 2 ^b	Day 8	Day 15	Day 22	Day 29	Day 57	Day 85	Day 113	Day 140 ^m	Day 155	Day 169
Overnight Residency	X ^a	X ^a	X ^a											
Informed Consent	X													
Review Inclusion/Exclusion Criteria	X	X												
Medication and Medical History	X ^c													
Weight/BMI & Temperature	X	X	X	X		X		X		X		X	X	X
Orthostatic Standing Test including supine blood pressure ^d		X ^d	X ^d	X ^d		X ^d		X ^d		X ^d		X ^d	X ^d	X ^d
Supine blood pressure ^e	X ^e				X ^e		X ^e		X ^e		X ^e			
24 hour blood pressure monitoring ^f		X ^f				X ^f		X ^f		X ^f				X ^f
ECG (12-lead)		X												X
Physical Examination ^g		X ^g	X ^g	X ^g		X ^g		X ^g		X ^g		X ^g	X ^g	X ^g
Urine Pregnancy Test ^h	X ^h													
Safety labs: Hematology, Chemistry, and UA	X ^o													X
PK Sampling ⁱ			X ⁱ	X ⁱ		X ⁱ		X ⁱ		X ⁱ		X ⁱ		X ⁱ
DHPG Sampling ^j			X ^j	X ^j				X ^j						
NE Sampling ^k			X ^k					X ^k						
OHQ (OHSA and OHDAS) ^l		X ^l	X ^l	X ^l	X ^l	X ^l	X ^l	X ^l	X ^l	X ^l	X ^l	X ^l	X ^l	
Clinician's/Subject's Global Impression ^l		X ^l	X ^l	X ^l	X ^l	X ^l	X ^l	X ^l	X ^l	X ^l	X ^l	X ^l	X ^l	
Concomitant Medications	X	X	X	X	X	X	X	X	X	X	X	X	X	X
Adverse Events	X	X	X	X	X	X	X	X	X	X	X	X	X	X
Study Drug Administration ^m			X ^m	X ^m	X ^m	X ^m	X ^m	X ^m	X ^m	X ^m	X ^m	X ^m	X ^m	
Subject Satisfaction Survey ⁿ			X ⁿ			X ⁿ		X ⁿ				X ⁿ		
Telephone Assessments (highlighted in gray)					X		X		X		X			

SCHEDULE OF STUDY ASSESSMENTS (CONTINUED)

- a. Subjects will admit to the research unit on Day -2 and remain resident through the completion of study procedures on the morning of Day 2.
- b. The timing of Day -1 "postdose" assessments should be prospectively calculated, based on the target Day 1 dosing time (eg, orthostatic standing test and Clinical Impression and OHQ assessments). Study Day 1 is defined as the day of first study dosing with TD-9855 in Part C. On Day 2 subjects are discharged from the research facility after all study procedures are completed the morning of Day 2.
- c. History update, if any changes since participation in Part A (and B if appropriate) of the study.

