- d. The orthostatic standing test will be performed in the morning before eating breakfast at approximately the same time of day each visit under fasting conditions after midnight to avoid the confounding effect of post-prandial hypotension. In addition, at least 4 hours after dosing (but no more than 7 hours) and before lunch, the standing test will be repeated. At each time point, BP and HR measurements will be recorded with automated (or manual) sphygmomanometer while supine at 5 and 10 min (with the torso and head elevated 30 degrees from horizontal), after seated at 5 and 10 min and after 1, 3, 5, and 10 min while standing. The standing time will be measured with a chronometer and the duration of standing will be recorded. More details related to the sequence of dosing and orthostatic assessments are described below. For the Day 155 and 169 assessments, the timing of the "postdose" orthostatic test should be calculated based on the Day 1 dosing time.
- e. On Days 8, 22, 57 and 113, supine blood pressures will be collected twice in the morning before eating (after 5 and 10 minutes resting at 30° elevation), and twice again at least 4 hours after dosing (but no more than 7 hours and before lunch) after 5 and 10 minutes resting at 30° elevation. On Day -2, supine blood pressures should be measured (after 5 and 10 minutes resting at 30° elevation).

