4.2 Exclusion Criteria

1. Systemic illnesses known to produce autonomic neuropathy, including but not limited to diabetes mellitus, amyloidosis, and autoimmune neuropathies.
2. Known intolerance to other NRIs or SNRIs.
3. Pre-existing sustained hypertension (BP \geq 150/100 mm Hg in the sitting position determined from three independent assessments, and not explained by the use of pressor agents).
4. Concomitant use of vasoconstricting agents for the purpose of increasing BP such as ephedrine, dihydroergotamine, or midodrine must stop taking these drugs at least 2 days or five half-lives (whichever is longer) prior to dosing on Day 1 of Part A and C, and throughout the duration of Part C. Subjects previously enrolled in Part A under previous versions of the protocol will continue taking fludrocortisone during the washout period and in Part C at the dose and regimen used in Part A. For new subjects enrolling in Part A under Amendment 3, fludrocortisone use in both Parts of the study and during the washout period will be limited to 0.1 mg QD.
5. Concomitant use of anti-hypertensive medication for the treatment of essential hypertension unrelated to autonomic dysfunction.
6. Have changed dose, frequency or type of prescribed medication, within two weeks of dosing on Day 1 with the following exceptions:

- Vasoconstricting agents such as ephedrine, dihydroergotamine, midodrine, or fludrocortisone
- Short courses (less than 2 weeks) of medications or treatments that do not interfere with, or exacerbate the subject's condition under study (eg, antibiotics)

7. Known or suspected alcohol or substance abuse within the past 12 months (DSM-IV definition of alcohol or substance abuse).
8. Clinically unstable coronary artery disease, or major cardiovascular or neurological event in the past 6 months.
9. Use of any monoamine oxidase inhibitor (MAO-I) within 14 days of dosing on Day 1.
10. History of untreated closed angle glaucoma, or treated closed angle glaucoma that, in the opinion of an ophthalmologist, might result in an increased risk to the subject.
11. Any significant uncontrolled cardiac arrhythmia.
12. Myocardial infarction in the past 6 months, or current unstable angina.
13. Congestive heart failure (NYHA Class 3 or 4).
14. Diabetes insipidus, insulin-dependent diabetes mellitus, or diabetic neuropathy.

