9.2.2 Secondary Efficacy Evaluation

For Part C, actual score and its change from baseline in composite OHSA, OHDAS, and OHQ will be generated descriptively by study visit. For Standing and Seated SBP, as well as duration of standing, the actual value (in minutes) and its change from baseline will also be summarized descriptively by time point (pre-breakfast, pre-lunch) and study visit. In addition, categorical shift (categories from 0 to 10 by 1 minute, and ≥ 10 minutes) of change from baseline for standing duration will also be summarized. For Standing SBP, number and percent of subjects with SBP > 80 mmHg by time point will also be analyzed.

For primary and secondary endpoints, graphic display of the data will be generated. Mean+/-SD line plot and boxplot will be used to depict the change over time point for vital signs and scores in OHSA, OHDAS and composite OHQ. Heatmap will be used to plot the individual change over time points on the data for vital signs (Seated, Standing, and Supine SBP and DBP). Bar chart will be used to depict the changes in scales of categorical data, e.g. OHSA scales, and in change subgroup for Seated SBP and Duration of Standing.

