9.3.4 Vital Signs

Vital signs will be summarized in terms of observed values (by time point), changes from baseline (by time point). When multiple values exist for the same nominal time point (e.g., duplicate reading), the average of the readings taken for vital signs will be used in the data analysis. All recorded values for vital signs data will be presented in a by-subject listing. Vital signs outliers will be flagged in the listing (Table 2).

Table 2. Vital Signs Outlier Thresholds

Heart Rate Systolic Blood Pressure		Diastolic Blood Pressure
(bpm) (mmHg)		(mmHg)
<40	<85	<45
>110	>160	>100

A sustained elevation in supine vital signs (the mean value of BP or HR) is defined as the elevation above a given threshold at three or more consecutive on-treatment measurements. For example, elevation at pre-breakfast, pre-lunch measurement on one visit as well as pre-breakfast measurement at the subsequent visit will be considered as

sustained elevation; on the other hand, elevation at pre-breakfast but not at pre-lunch for 3 consecutive visits will not constitute as "sustained" elevation.

Categorical elevated vital signs are defined in Table 3 and Table 4. Number of subjects with elevated vital signs will be summarized by visits in Part C.

Table 3. Threshold for Elevated Supine Vital Sign

Measurements	Thres	hold
Increase from Baseline in SBP	≥ 20	≥ 30
(mmHg)		
Increase from Baseline in DBP	≥ 10	≥ 20
(mmHg)		
Increase from Baseline in HR	≥ 10	≥ 20
(bpm)		
Post-baseline value SBP (mmHg)	≥ 140	≥ 160
Post-baseline value DBP (mmHg)	≥ 90	≥ 100
Post-baseline value HR (bpm)	≥ 100	≥ 120

Table 4. Combined Criteria for Elevated Supine Vital Sign

Combined Criteria
SBP ≥ 140 and Increase from Baseline ≥ 20
DBP ≥ 90 and Increase from Baseline ≥ 10
HR ≥ 100 and Increase from Baseline ≥ 20
SBP ≥ 160 and Increase from Baseline ≥ 20
DBP ≥ 100 and Increase from Baseline ≥ 10
HR ≥ 120 and Increase from Baseline ≥ 20

In addition, the following will also be summarized.

- a decrease in systolic blood pressure (a mean value of SBP) from supine to standing of ≥ 20 (and 30) mmHg and/or
- a decrease in diastolic blood pressure (a mean value of DBP) from supine to standing of ≥ 10 mmHg
- an increase in heart rate (a mean value of HR) from supine to standing of ≥ 30 bpm and/or
- an observed HR ≥ 120 bpm upon standing

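### Pre-lunch changes in BP, heart rate and standing duration are taken from a fasting pre-breakfast baseline, so they mix drug effect with the untreated morning-to-midday difference

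*SAP*

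**What the plan says.** SAP 6.2 defines two kinds of baseline. For OHQ scores and the Global Impressions, "baseline is defined as the pre-lunch measurement on Day -1". For the haemodynamic measures the rule differs: "For the blood pressure, heart rate, and duration of standing, baseline is defined as the pre-breakfast measurement on Day 1".

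SAP 9.2.2 states that seated and standing SBP and standing duration, with their changes from baseline, "will also be summarized descriptively by time point (pre-breakfast, pre-lunch) and study visit". SAP 9.3.4 likewise summarises changes in vital signs by time point. Its Table 3 counts subjects by, among other criteria, "Increase from Baseline in SBP", and Table 4 combines such increases with absolute values. No separate pre-lunch baseline is defined.

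In Protocol Table 2, footnote d, the morning standing test is done fasting, and "at least 4 hours after dosing (but no more than 7 hours) and before lunch, the standing test will be repeated". Footnote b sets the clock times of the nominally postdose tests on the untreated day before dosing: "assessments should be prospectively calculated, based on the target Day 1 dosing time (eg, orthostatic standing test and Clinical Impression and OHQ assessments"). For Days 155 and 169, footnote d says the postdose "orthostatic test should be calculated based on the Day 1 dosing time".

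**The concern.** The morning reading is fasting and untreated. The midday reading comes 4 to 7 hours after dosing, and in the illustrative visit sequence after Protocol Table 2 breakfast is eaten at dosing. The two readings therefore differ in clock time and meal state as well as in drug exposure. The protocol treats this as important: it requires fasting so that meals do not confound the test, and Protocol 3.4.1 words the Part C SBP endpoints as time-matched comparisons. SAP 5.1 replaces these with plain change from baseline.

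A sustained pressor response is part of the Part C objective (SAP 2.1), but the primary endpoint is a symptom item, so the pressor conclusion rests on these BP summaries. Pre-lunch is the only scheduled clinic time point 4 to 7 hours after dosing, and every Part C subject is on active drug. A positive untreated difference would look like a pressor effect. A negative one would hide a real effect, and could also hide real supine increases in the safety counts.

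**Working it through.** There is no figure in the plan to reproduce: the Part C sample size text is not shown, and the point does not depend on it.

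**Step 1: what the pre-lunch change estimates.** Let T be the drug effect at midday and d the untreated midday value minus the untreated fasting morning value.

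- SAP baseline: E[pre-lunch change] = T + d.
- Day -1 midday baseline: E[pre-lunch change] = T, apart from day-to-day variation.

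For an assumed T = 10 mmHg, the expected change under the SAP baseline is 0, 5, 10, 15 or 20 mmHg for d = -10, -5, 0, +5 or +10. With the matched baseline it is 10 mmHg throughout.

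**Step 2: which readings are affected (Protocol Table 2).**

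- On-treatment midday standing tests: Days 1, 15, 29, 85 and 140.
- Supine-only midday readings: Days 8, 22, 57 and 113.
- Follow-up midday tests: Days 155 and 169.

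Not affected: OHSA question 1, actual values, absolute-value thresholds, and pre-breakfast changes where the morning test precedes dosing.

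**Step 3: effect on a planned count.** Take the SAP Table 3 criterion of a supine SBP increase of at least 20 mmHg, for one pre-lunch reading. Assume Normal changes with standard deviation SD:

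P(change ≥ 20) = 1 − Φ((20 − T − d)/SD).

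For example, with T = 0, SD = 15 and d = +10, this is 1 − Φ(10/15) = 25.2%.

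| T, SD (mmHg) | d = -10 | -5 | 0 | +5 | +10 |
|---|---|---|---|---|---|
| 0, 10 | 0.1% | 0.6% | 2.3% | 6.7% | 15.9% |
| 0, 15 | 2.3% | 4.8% | 9.1% | 15.9% | 25.2% |
| 0, 20 | 6.7% | 10.6% | 15.9% | 22.7% | 30.9% |
| 10, 15 | 9.1% | 15.9% | 25.2% | 36.9% | 50.0% |

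At T = 0 and SD 15, 9.1% is ordinary variability. The part due to the baseline runs from 2.3 − 9.1 = −6.8 to 25.2 − 9.1 = +16.1 percentage points. For the 30 mmHg criterion, P(change ≥ 30) at T = 0 and SD 15 is 0.4%, 1.0%, 2.3%, 4.8% and 9.1% across the same d. T, d and SD are all assumptions; the documents give none of them.

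**Step 4: is a matched reading available?** Table 2 marks the standing test, which includes supine BP, on Day -1. Footnotes b and d together give an untreated morning test and an untreated test at the Day 1 postdose clock time. Both the matched baseline and d itself can be computed from scheduled data.

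**Step 5: cost of using Day -1.** Protocol 4.2, criterion 4, requires vasoconstrictors to be stopped "at least 2 days or five half-lives (whichever is longer) prior to dosing on Day 1 of Part A and C". On the illustrative clock times (test at 12:00, dose at 8:00), Day -1 midday is 20 h before Day 1 dosing. For a half-life of h hours, the half-lives elapsed by then are at least (max(48, 5h) − 20)/h. The minimum is at h = 48/5 = 9.6, giving 28/9.6 = 2.92. Under first-order elimination at most 2^(−2.92) = 13% remains, against 2^(−5) = 3% at Day 1 dosing.

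**The case against.** The last reading before first dose is a defensible baseline, and the data needed to judge d are not lost. SAP 9.2.2 and 9.2.3 present actual values by time point, Days 155 and 169 are off drug and clock-timed, and 24-hour monitoring covers Day -1 where equipment permits. The midday test is at least 4 hours after dosing and before lunch, which limits any meal effect. The sustained-elevation rule in SAP 9.3.4 needs three consecutive readings, and under the schedule any such run includes a pre-breakfast one. A positive d alone therefore cannot create a sustained elevation. Table 4 also requires an absolute value. Day -1 midday falls before the washout limit, so one possible bias is exchanged for another. Part C is descriptive, and without a control arm regression to the mean, day-to-day variation and open-label effects remain.

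Most of this is right and limits the severity. It does not correct the planned outputs: the pre-lunch change tables and increase-from-baseline counts still contain d. Several change-table titles in SAP Appendix 2 refer to the period after dosing, so Day -1 rows are not assured. Any run of three readings also includes a pre-lunch one, so a negative d can break a true sustained elevation. The washout point is real and is the reason to keep the Day 1 baseline as a sensitivity analysis, but SAP 6.2 already accepts Day -1 midday for the baseline of the primary endpoint.

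**Conclusion.** The concern holds. As written, pre-lunch changes in BP, heart rate and standing duration estimate drug effect plus an untreated morning-to-midday difference of unknown size and sign. The shift is one for one in the mean at any sample size. The percentages in the working only illustrate how sensitive the counts are; they rest on assumed d, SD and Normality. That the two components are mixed follows from the SAP and Table 2 alone. The SAP should be corrected, but the flaw is not fatal: the primary endpoint is untouched, and pre-breakfast changes, actual values and 24-hour monitoring give partial protection. A matched baseline removes only the time-of-day and meal component.

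**What to change.** In SAP 6.2, define the BP, heart rate and standing-duration baseline by time point: Day 1 pre-dose for pre-breakfast readings, and the Day -1 test at the Day 1 postdose clock time for pre-lunch readings.

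- Apply it to all pre-lunch changes and to the pre-lunch increase-from-baseline criteria in SAP Tables 3 and 4. In a sustained-elevation run, compare each reading with its own time-matched baseline.
- Tabulate the Day -1 morning-to-midday difference.
- Keep the Day 1 pre-breakfast baseline for pre-lunch changes as a sensitivity analysis. A subject without a Day -1 midday test stays in that analysis.
- State that the SAP 7.3 subgroups for orthostatic hypotension (already fixed at Day 1 pre-breakfast) and standing duration, and the SAP 9.1.2 baseline summaries, remain on Day 1 pre-breakfast.

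The cost is SAP wording, one derived-baseline flag and one small table, with no new visits or procedures. The downside is the earlier position of Day -1 relative to the washout limit.

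A separate point is not cured by this change. Footnote m of Protocol Table 2 has the dose taken after the morning test on visit days, but at home before travel when the subject travels to the clinic. These sentences must be reconciled, and morning readings classified as pre-dose or post-dose from recorded times.
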